- For each AE/SAE, the investigator **must** document in the medical notes that he/she has reviewed the AE/SAE and has provided an assessment of causality.
- With regard to assessing causality of SAEs:
 - There may be situations in which an SAE has occurred and the investigator has minimal information to include in the initial report. However, the causality assessment is one of the criteria used when determining regulatory reporting requirements. **Therefore, it is very important that the investigator always make an assessment of causality based on the available information for every event before the initial transmission of the SAE.**
 - The investigator may change his/her opinion of causality in light of follow-up information and submit the updated causality assessment.

Follow-Up of Adverse Events and Serious Adverse Events

- The investigator is obligated to perform or arrange for the conduct of supplemental measurements and/or evaluations as medically indicated or as requested by the sponsor to elucidate the nature and/or causality of the AE or SAE as fully as possible. This may include additional laboratory tests or investigations, histopathological examinations, or consultation with other health care professionals.
- Once an AE is detected, it should be followed in the AE eCRFs until it has resolved, has stabilized, or until it is judged to be permanent; assessment should be made at each visit (or more frequently if necessary) of any changes in severity, the suspected relationship to the study drug, the interventions required to treat the event, and the outcome.
- When the severity of an AE changes over time for a reporting period (eg, between visits), each change in severity will be reported as a separate AE.
- If a participant dies during participation in the study or during a recognized follow-up period, the investigator will provide the sponsor with a copy of any postmortem findings, including histopathology.
- Updated SAE information will be recorded in the originally completed eCRF and reported to Incyte Pharmacovigilance until resolution, stabilization, the event is otherwise explained, or the participant is lost to follow-up.
- Any updated SAE data (including SAEs being downgraded to nonserious) will be submitted to the sponsor (or designee) within 24 hours of receipt of the information.

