13.1 Adverse Events

Adverse events (AEs) will be coded according to the Medical Dictionary for Regulatory Activities (MedDRA), Version 24.0.

Treatment emergent adverse events (TEAEs) are derived as any AEs with onset date during or after the first study treatment dose. AEs starting on the first study treatment dosing date and related

	STATISTICAL ANALYSIS PLAN, Version Final v1.0
Protocol Number: INCB 18424-901	Sponsor: Incyte Corporation
Study Title: An Open-Label, Single-Arm Study to Evaluate the Effect of Ruxolitinib 1.5% Cream on Itch in Adult Participants With Atopic Dermatitis (SCRATCH-AD)	

to a pre-dose study assessment will not be considered as TEAE. See [Appendix 2](#) for handling of completely or partially missing dates for AEs. In the case where it is not possible to define an AE as treatment emergent or not, the AE will be classified as treatment emergent.

An overall summary table of adverse events will be provided. The number of events and the number and percentage of participants who experienced AE, TEAE, TEAE at application site, TEAE by relationship, TEAE by toxicity grade, related TEAE by toxicity grade, TEAE of CTCAE Grade 3 or higher, serious TEAE, serious TEAE by toxicity grade, TEAE leading to study drug interruption, TEAE leading to study drug discontinuation, TEAE leading to study discontinuation and AE leading to death will be presented.

Unless otherwise specified, a participant experiencing the same TEAE multiple times will be counted only once for the corresponding PT. Similarly, if a participant experiences multiple TEAEs within the same SOC, the participant will be counted only once for that SOC. TEAEs will be sorted alphabetically by SOC and within each SOC the PT will be presented by decreasing order.

Frequency and percentage of participants who experience TEAE will be summarized by SOC and PT within SOC.

Frequency and percentage of participants who experience TEAE will be summarized by SOC, PT and relationship (causality). A treatment-related AE is defined as any TEAE that is assessed by the Investigator as possibly related to study treatment. TEAE that is assessed as not possibly related will be defined as not treatment-related. TEAE with an unknown relationship will be considered as treatment-related. If a participant experiences more than one TEAE within different relationship categories within the same SOC/PT, the participant will be counted once for that SOC/PT in each relationship category.

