Frequency and percentage of participants who experience TEAE will be summarized by SOC, PT and intensity grade. TEAE with an unknown intensity grade will be considered missing. If a participant experiences more than one TEAE within different intensity grade categories within the same SOC/PT, the participant will be counted once for that SOC/PT in each intensity grade category. Similarly, frequency and percentage of participants who experience treatment-related TEAE will be summarized by SOC, PT and intensity grade.

Frequency and percentage of participants who experience serious TEAE will be summarized by SOC and PT within SOC.

Frequency and percentage of participants who experience TEAE of intensity of Grade 3 or higher will be summarized by SOC and PT within SOC.

Frequency and percentage of participants who experience serious TEAE will be summarized by SOC, PT and intensity grade. TEAE with an unknown intensity grade will be considered missing.

	STATISTICAL ANALYSIS PLAN, Version Final v1.0
Protocol Number: INCB 18424-901	Sponsor: Incyte Corporation
Study Title: An Open-Label, Single-Arm Study to Evaluate the Effect of Ruxolitinib 1.5% Cream on Itch in Adult Participants With Atopic Dermatitis (SCRATCH-AD)	

If a participant experiences more than one TEAE within different intensity grade categories within the same SOC/PT, the participant will be counted once for that SOC/PT in each intensity grade category.

Frequency and percentage of participants who experience Application Site TEAE will be summarized by SOC and PT.

Frequency and percentage of participants who experience TEAE of Application site pain Preferred Term will be summarized by Lowest Level Term.

Listings of all AEs, all AEs leading to death, all serious AEs, all TEAEs leading to study treatment discontinuation, all TEAEs leading to study treatment interruption and all TEAEs leading to study discontinuation will be provided. A listing of drug overdose will be provided.

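### AE grade tables count a participant in every grade reached and severity changes count as separate events, so worst grade per participant, especially for local AEs, is not shown

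*SAP*

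**What the plan says.** SAP section 13.1 plans a table by grade: "Frequency and percentage of participants who experience TEAE will be summarized by SOC, PT and intensity grade". Treatment-related and serious TEAEs get the same kind of table. For a participant with TEAEs of different grades under one SOC/PT, the rule is that "the participant will be counted once for that SOC/PT in each intensity grade category". No maximum-grade rule is given. In tables not split by grade the default differs: "a participant experiencing the same TEAE multiple times will be counted only once for the corresponding PT".

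Protocol section 9.3 sets the recording rule. When the severity of an AE changes within a reporting period, "each change in severity will be reported as a separate AE". The overall summary in SAP section 13.1 then gives "The number of events and the number and percentage of participants who experienced AE, TEAE, TEAE at application site", followed by further categories that include TEAEs by toxicity grade. It does not say whether records of one fluctuating AE are joined before events are counted, or how participants are counted by grade in that summary.

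For local events, "Frequency and percentage of participants who experience Application Site TEAE will be summarized by SOC and PT", and application site pain is broken down by Lowest Level Term. Neither table is by grade. Separately, "TEAE of intensity of Grade 3 or higher will be summarized by SOC and PT within SOC".

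The secondary safety endpoint (Protocol section 3, Table 4; SAP section 2) covers both the occurrence and the severity of local and systemic AEs.

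**The concern.** Severity is a named part of the only safety endpoint. The usual summary of it is the number of participants whose worst event was Grade 1, Grade 2 and so on, with each participant appearing once. The planned rows are not mutually exclusive, so they do not give this.

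A participant can enter more than one row in two ways: through one event that changes grade, or through separate episodes of the same PT at different grades. The first way also adds events, because the recording rule turns one fluctuating AE into several records and the event count takes them as they come.

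The study has a single arm, so no comparator is counted under the same rule and the absolute counts are themselves the result. A reader who takes the grade rows as a distribution, or the number of events as a number of episodes, would be misled. For local tolerability of a cream, the direct summary (participants by worst application-site grade) is not planned.

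**Working it through.** The plan states no figure to reproduce. The check applies the written rules to assumed AE courses.

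**Inputs from the documents**
- Grade tables: one entry per participant for each grade reached within a SOC/PT (SAP 13.1).
- Records: one per severity change within a reporting period (Protocol 9.3).
- Events: number of records, since no linking rule is given (SAP 13.1).

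**Assumed, not in the documents:** ten participants, one episode each of the same PT. Three stay at Grade 1, six go 1-2-1, and one goes 1-2-3-2-1.

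**Events.** Planned: 3×1 + 6×3 + 1×5 = 26. One per episode: 10.

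**Participants by grade**

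| Row | Every grade reached (planned) | Maximum grade |
|---|---|---|
| Grade 1 | 3 + 6 + 1 = 10 | 3 |
| Grade 2 | 6 + 1 = 7 | 6 |
| Grade 3 | 1 | 1 |
| Sum of rows | 18 | 10 |

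The Grade 3 row is the same under both methods, and so is the Grade 3-or-higher participant count (1). The excess lies in the rows below each participant's worst grade. Grade 3's share of entries falls from 1/10 = 10.0% to 1/18 = 5.6%.

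**Range.** Vary the number with a 1-2-1 course, keep the one 1-2-3-2-1 course, and leave the rest at Grade 1:
- none: 9 + 5 = 14 events; rows sum to 10 + 1 + 1 = 12
- three: 6 + 9 + 5 = 20 events; rows sum to 10 + 4 + 1 = 15
- six: 26 events; rows sum to 18

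Maximum-grade counting gives 10 and 10 each time. If no grade ever changes, the two methods agree.

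**How far the profile reads milder.** The share at the highest grade falls in all three cases. Not every summary moves that way. With no 1-2-1 courses, entries above Grade 1 are 2/12 = 16.7% under the planned rule against 1/10 = 10.0% at maximum grade. An assumed 3-4-3 course gives three Grade 3-or-higher records for one episode and puts the participant in both the Grade 3 and Grade 4 rows, but only once in the Grade 3-or-higher participant table.

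**Can worst grade be recovered from the tables?** For one PT with only Grades 1 and 2, and no missing grades, it can: worst Grade 2 is the Grade 2 row, and worst Grade 1 is the any-grade count minus that row. With three grades it cannot in general. In the example the published counts would be 10 with the PT, 7 in the Grade 2 row and 1 in the Grade 3 row. If the Grade 3 participant is also in the Grade 2 row, worst Grades 1/2/3 are 3/6/1; if not, they are 2/7/1. The tables do not say which. Across several application-site PTs the problem is greater, since the same participant may appear under more than one PT.

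**Likely size here.** Protocol section 2.2.2 gives TEAE rates for the first part (to Week 8) of two Phase 3 studies. The most common TEAE reached 3.0% and 2.1%, and application site pain 1.0% and 1.5%. For 48 participants, 48 × 0.030 = 1.4 and 48 × 0.015 = 0.7. Ten participants with one PT would be 10/48 = 20.8%, so the example shows how the rule works and is not a forecast.

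**The case against.** The strongest reply is that this is largely a matter of presentation. The rule is explicit, is set in advance and matches the SAP's rule for the relationship tables. The study is descriptive, and no estimate, test or decision depends on it. The most important severity output, participants with Grade 3 or higher TEAEs, counts each participant once per PT and per SOC. A listing of all AEs is planned, so worst grades can be rebuilt by hand for about 48 participants. Event counts stand beside participant counts. Record handling may be settled in the eCRF guidelines, and table layouts are in a separate document; neither was available.

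Most of this stands, and it limits the size of the point. It does not remove it, because a listing is not a planned summary of an endpoint and the overlapping rows are what would be reported.

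Three stronger readings are tempting, and the documents do not support them:
- **That severity is inflated.** The rule moves nobody above their worst grade. It adds entries below it.
- **That local AEs have no grade table.** The all-TEAE table by SOC, PT and grade includes application-site PTs, as would the treatment-related one for related events. What is missing is a local subset by grade and a count of participants by worst local grade.
- **That incidence is overstated.** In tables without grade, each participant counts once per PT and once per SOC.

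**Conclusion.** The point holds as a reporting weakness. Under the plan as written, grade rows overlap, lower-grade rows and event counts can be overstated, and participants by worst local grade across PTs cannot be read from any planned table. Any-grade incidence and the Grade 3-or-higher participant table are unaffected by these counting rules.

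The size depends on how often AEs change grade or recur at another grade, which the documents do not give. At the Phase 3 rates, over 28 days and in about 48 participants, few rows are likely to overlap, so the effect is probably small. The conclusion also assumes that the eCRF guidelines and table layouts contain no linking or maximum-grade rule beyond what the SAP states. The change is worth making because it is cheap, uses data already collected and gives the endpoint its direct summary.

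**What to change.** In SAP section 13.1:

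1. In the TEAE, treatment-related TEAE and serious TEAE grade tables, and in the overall summary, count each participant once at maximum CTCAE grade per PT, per SOC and overall. State how a participant with a missing grade is placed.
2. Add a table of application-site TEAEs by PT and maximum grade, with an overall row for any application-site TEAE.
3. For event counts, treat severity-change records of the same AE as one event at its maximum grade where the eCRF allows them to be linked. Where it does not, label the counts as severity records rather than events.
4. Do not label every TEAE outside the application site as systemic. The documents do not define it that way, and events at biopsy or suture sites would be misclassified.

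The cost is a change of SAP wording, minor reprogramming and one added table. No new data are needed. Linking records may not be possible, which is why item 3 offers a labelling alternative.

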13.2 Clinical Laboratory

Descriptive statistics will be presented for data related to serum chemistry, hematology and quantitative urinalysis. Change from baseline values will be presented for each post-baseline assessment. Frequencies and percentages for each result will be provided for qualitative urinalysis data.

Shift tables from baseline to each post-baseline visits describing shifts to abnormality will be provided as well based on abnormality in the CRF. Only participants with a baseline result and a result at the specified visit for the parameter will be considered.

Separate listings of all data for serum chemistry, hematology and urinalysis will be provided. Pregnancy tests results will be listed.

In addition, separate listings of data for serum chemistry, hematology and urinalysis will be provided for each parameter where a participant had at least one abnormal clinically significant result.

13.3 Vital Signs

Descriptive statistics will be presented for data related to vital signs (systolic blood pressure diastolic blood pressure, pulse, respiratory rate and body temperature). A listing of all vital signs assessments will be provided.

	STATISTICAL ANALYSIS PLAN, Version Final v1.0
Protocol Number: INCB 18424-901	Sponsor: Incyte Corporation
Study Title: An Open-Label, Single-Arm Study to Evaluate the Effect of Ruxolitinib 1.5% Cream on Itch in Adult Participants With Atopic Dermatitis (SCRATCH-AD)	

15 APPENDICES

Appendix 1

Output Conventions

TLF will be generated using SAS® and will be displayed on letter size paper with landscape orientation, 1 inch margins and 9 pt Courier New font.

The header section will comprise the Sponsor's name, the protocol number, the delivery description, the data cut-off date (if applicable), the TLF number, the TLF title, the analysis set, and the page number (Page X of Y). The footer section will include the TLF footnotes, the CRO's name, the date and time of the execution of the program, the reference listings and the name of the program.

Mean, median and quantiles will be displayed to one more decimal place than the original value; minimum and maximum will keep the same number of decimal places as the original value; standard deviation, standard error and CI will be displayed to two more decimal places than the original value. If derived parameters are to be summarized, the number of decimals of the derived values is to be chosen on a case-by-case basis, but the rule above applies.

For categorical summary tables, percentages will be reported to one decimal place. Percentages between 0 and 0.1 (both exclusive) will be displayed as “<0.1”. The denominator for each percentage will be the number of participants within the population per treatment group unless otherwise specified.

Listings will be ordered by participant number, date and visit (where applicable). Imputed dates will not be presented in the listings.

Dates & Times Format

Date and time (if available) will be presented in the format yyyy-mm-dd/hh:mm.

Presentation of Treatment Groups

When applicable, study treatments will be represented as follows in the different outputs:

Study Treatment Full Name	Study Treatment Output Name
Ruxolitinib 1.5% BID	Ruxolitinib

	STATISTICAL ANALYSIS PLAN, Version Final v1.0
Protocol Number: INCB 18424-901	Sponsor: Incyte Corporation
Study Title: An Open-Label, Single-Arm Study to Evaluate the Effect of Ruxolitinib 1.5% Cream on Itch in Adult Participants With Atopic Dermatitis (SCRATCH-AD)	

Appendix 2

Algorithm for Imputation of Start/End Date of Adverse Events, Prior/Concomitant Medications and Prior/Concomitant Non-Drug Therapies and Surgical Procedures

Event Start Date Imputation

- Imputation of event end date should be done before imputation of event start date.
- Completely missing: Impute to the first study treatment date.
- Missing day and month: Impute to January 1st, unless year is the same as year of first study treatment dose then impute to the first study treatment date.
- Missing day: Impute to the 1st of the month, unless month and year are the same as month and year of first study treatment dose then impute to the first study treatment date.
- If imputed event start date is after event end date (imputed or not), set the event start date to the imputed event end date.

Event End Date Imputation

- Completely Missing: Impute to the last contact date.
- Missing day and month: Impute to December 31st, unless year is the same as last contact date then impute to the last contact date.
- Missing day: Impute to the last day of the month, unless year and month are the same as year and month of last contact date then impute to the last contact date.

	STATISTICAL ANALYSIS PLAN, Version Final v1.0
Protocol Number: INCB 18424-901	Sponsor: Incyte Corporation
Study Title: An Open-Label, Single-Arm Study to Evaluate the Effect of Ruxolitinib 1.5% Cream on Itch in Adult Participants With Atopic Dermatitis (SCRATCH-AD)	

Appendix 3

Scoring Method for the Abbreviated 9-Item Treatment Satisfaction Questionnaire for Medication (TSQM-9)

Scores for each domain are computed by adding the TSQM items in each domain and then transforming the composite score into a value ranging from 0 to 100. Of note, a score can be computed for a domain only if no more than one item is missing from that domain. The calculations specific to each domain are presented in detail below.

1. Global Satisfaction

$([\text{Sum}(Item\ 7\ \text{to}\ Item\ 9) - 3] \text{ divided by } 14) * 100$

If either Item 7 or 8 is missing

$([\text{Sum}(\text{the two completed items}) - 2] \text{ divided by } 10) * 100$

If Item 9 is missing

$([\text{Sum}(Item7\ \text{and}\ Item8)) - 2] \text{ divided by } 8) * 100$

2. Effectiveness

$([\text{Item}\ 1 + \text{Item}\ 2 + \text{Item}\ 3) - 3] \text{ divided by } 18) * 100$

If one item is missing

$([\text{Sum}(\text{the two completed items} - 2] \text{ divided by } 12) * 100$

3. Convenience

$([\text{Sum}(Item\ 4\ \text{to}\ Item\ 6) - 3] \text{ divided by } 18) * 100$

If one item is missing

$([\text{Sum}(\text{the two completed items}) - 2] \text{ divided by } 12) * 100$

	STATISTICAL ANALYSIS PLAN, Version Final v1.0
Protocol Number: INCB 18424-901	Sponsor: Incyte Corporation
Study Title: An Open-Label, Single-Arm Study to Evaluate the Effect of Ruxolitinib 1.5% Cream on Itch in Adult Participants With Atopic Dermatitis (SCRATCH-AD)	

Appendix 4

Scoring Method for the Eczema Area and Severity Index

Four anatomic sites (head, upper extremities, trunk, and lower extremities) are assessed for erythema, induration/infiltration (papules), excoriation, and lichenification as seen on the day of the examination. The severity of each sign is assessed using the following 4-point scale (half steps are allowed; eg, 0.5, 1.5, and 2.5):

- 0 = none
- 1 = mild
- 2 = moderate
- 3 = severe

The area affected by AD within a given anatomic site is estimated as a percentage of the total area of that anatomic site and assigned a numerical value according to the degree of AD involvement as follows:

- 0 = no involvement
- 1 = < 10%
- 2 = 10% to < 30%
- 3 = 30% to < 50%
- 4 = 50% to < 70%
- 5 = 70% to < 90%
- 6 = 90% to 100%

The EASI score is obtained by using the following formula:

$$\text{EASI} = 0.1 (E_h + I_h + Ex_h + L_h) A_h + 0.2 (E_u + I_u + Ex_u + L_u) A_u + 0.3 (E_t + I_t + Ex_t + L_t) A_t + 0.4 (E_l + I_l + Ex_l + L_l) A_l.$$

Where E, I, Ex, L, and A denote erythema, induration, excoriation, lichenification, and area, respectively, and h, u, t, and l denote head, upper extremities, trunk, and lower extremities, respectively.

The EASI score will be set as missing if at least one question value is missing.

Certificate Of Completion

Envelope Id: 31209E82CF1543459D8C78912BEA71F8

Status: Completed

Subject: Your electronic signature is required by [REDACTED] - INCB_18424-901_SAP_Final_v1.0

Source Envelope:

Document Pages: 32

Signatures: 4

Envelope Originator:

Certificate Pages: 6

Initials: 0

[REDACTED]

AutoNav: Enabled

[REDACTED]

EnvelopeD Stamping: Enabled

[REDACTED]

Time Zone: (UTC-05:00) Eastern Time (US & Canada)

[REDACTED]

IP Address: [REDACTED]

Record Tracking

Status: Original

Holder: [REDACTED]

Location: DocuSign

05-Oct-2022 | 15:37

Signer Events

Signature

Timestamp

Security Level: Email, Account Authentication
(Required)

Signature Adoption: Pre-selected Style

Sent: 05-Oct-2022 | 15:44

Signature ID:

Viewed: 05-Oct-2022 | 16:08

Using IP Address: [REDACTED]

Signed: 05-Oct-2022 | 16:09

With Signing Authentication via DocuSign password

With Signing Reasons (on each tab):

I am the author of this document

Electronic Record and Signature Disclosure:

Accepted: 27-May-2022 | 15:39

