5.1. Inclusion Criteria

Participants are eligible to be included in the study only if all of the following criteria apply:

1. Male or female participant aged 18 to 65 years, inclusive, at screening.
2. Participant is able to comprehend and willing to sign a written ICF for this study.
Note: Consent must be obtained prior to any study-related procedures.
3. Participant has clinically confirmed diagnosis of active AD according to Hanifin and Rajka (1980) criteria (see [Appendix B](#)).
4. Participant has at least a 6-month history of AD (information obtained from medical chart, participant's physician, or directly from the participant).
5. Participant has chronic pruritus related to AD for at least 3 months before the screening visit (information obtained from medical chart, participant's physician, or directly from the participant).
6. Participant has an overall BSA (excluding palms, soles, scalp, genitals, and folds) affected by AD of 1% to 20% on Day 1.
7. Participant has an IGA score of at least 2 on Day 1.
8. Participant has 1 target AD lesion on Day 1 that can allow for the collection of skin samples as per study requirement (excluding face, scalp, genitals, axillae, groin, folds, palms, and soles). The target lesion should be representative of the participant's overall disease and should be treated with study drug.

Note: A target lesion that could accommodate all skin samples (tape strips, biopsies, and skin microbiome) and TEWL assessment is the preferred scenario. However, a second target lesion could be selected, if needed. If selecting 2 target lesions on Day 1, they should be of similar severity and preferably from the same anatomical region.

9. Participant has a single PP-NRS score ≥ 4 in the 24-hour period prior to the screening visit.
10. Participant must be willing to complete the once-daily PP-NRS (24-hour recall period) entries at approximately the same time each day during the study (from screening to Day -1 and from Day 2 to the Day 29 visit).

Note: Inclusion of participants completing fewer than 4 of 7 daily PP-NRS questionnaires during the last 7 days of the screening period (run-in period) must be approved by the sponsor.

11. Prior to the first application of study drug, participant has a baseline mean PP-NRS (24-hour recall period) score ≥ 4.0 during the run-in period, defined as the average of all nonmissing scores reported during the 7-day run-in period.

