6.2 Handling of Dropouts or Missing data

No imputation will be made for efficacy data. See [Appendix 2](#) for handling of completely or partially missing dates for prior and concomitant medications and adverse events.

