12.2.5 Secondary Endpoints Analysis

Descriptive statistics will be presented for all secondary efficacy endpoints, by visit and timepoint (if applicable). The change from baseline and percent change from baseline in PP-NRS, mPP-NRS and IGA, and proportion endpoints for PP-NRS, mPP-NRS, and IGA-TS, will be analyzed descriptively at each visit. The 95% CI will be provided for the mean change, percent change and the proportions (using the Clopper-Pearson method). For proportion endpoints, percentages will be based on the number of participants with a response at the specified visit and timepoint.

The proportion of participants achieving an IGA score of 0 or 1 and associated 95% CI (using the Clopper-Pearson method) will also be reported descriptively.

The time to MCID will be analyzed using Kaplan Meier estimation for PP-NRS and mPP-NRS. A participant will be considered censored if he has not met the event of interest at the end of the study or if the participant is lost to follow up at last observation. Those participants will be censored at their last available mPP-NRS or PP-NRS assessment date or time. Survival curves will also be presented.

A line graph presenting the value and a line graph presenting the change from baseline in mPP-NRS over time will be produced. The value and change from baseline in PP-NRS over time and value and change from baseline in IGA will be presented similarly.

	STATISTICAL ANALYSIS PLAN, Version Final v1.0
Protocol Number: INCB 18424-901	Sponsor: Incyte Corporation
Study Title: An Open-Label, Single-Arm Study to Evaluate the Effect of Ruxolitinib 1.5% Cream on Itch in Adult Participants With Atopic Dermatitis (SCRATCH-AD)	

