12.4.3 Eczema Area and Severity Index

The Eczema Area and Severity Index (EASI) is a composite score ranging from 0 to 72 that takes into account the degree of erythema, induration/infiltration (papules), excoriation, and lichenification (each scored from 0 to 3 separately) for each of 4 body regions, with adjustment for the percentage of BSA involved for each body region and for the proportion of the body region to the whole body. Scoring method for the Eczema Area and Severity Index is presented in [Appendix 4](#).

Descriptive statistics for the EASI will be presented by visit, and the corresponding change and percent change from baseline when appropriate. The 95% CI will be provided for the mean change and percent change.

Additionally, the proportion of participants with at least a 75% reduction from baseline in EASI (EASI-75) and associated 95% CI (using the Clopper-Pearson method) will be reported descriptively.

All EASI assessments will be listed. A line graph presenting the value in EASI and a line graph presenting the change from baseline in the EASI over time will be produced.

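### SAP Appendix 4 sets the EASI to missing for any missing item, with no exception for a region whose area score of 0 makes its severity items irrelevant

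*SAP*

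**What the plan says.** SAP Appendix 4 defines the EASI as four regional terms. Each is a weight times the sum of four severity grades times an area score; the head term is "0.1 (E_h + I_h + Ex_h + L_h) A_h". The area scale starts at "0 = no involvement", and the severity scale also has a grade of 0 for an absent sign. The appendix ends with the missing-item rule: "The EASI score will be set as missing if at least one question value is missing". The rule is unconditional. Protocol Appendix D gives the same formula and has no missing-item rule.

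SAP 12.4.3, under Other Analyses, reports the EASI, its change and percent change with 95% CIs, EASI-75 with a Clopper-Pearson interval, and line graphs. SAP 6.2 adds: "No imputation will be made for efficacy data".

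Two denominator rules could apply to EASI-75. SAP 12.2.5, on the secondary endpoints, states: "For proportion endpoints, percentages will be based on the number of participants with a response at the specified visit and timepoint". SAP Appendix 1 makes the analysis population the default denominator unless otherwise specified. SAP 12.4.3 does not choose between them.

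Protocol Section 5.1, criterion 6, requires an overall BSA "affected by AD of 1% to 20% on Day 1", not counting palms, soles, scalp, genitals and folds. Protocol Table 3 schedules the EASI on Day 1, Day 15, Day 29 and at early termination, with none at screening.

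**The concern.** The missing-item rule does not fit the formula above it. When a region's area score is 0, its severity grades are multiplied by 0 and cannot affect the total. A blank among them loses no information, yet the rule discards the whole score.

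With entry limited to 20% BSA by the eligibility measure, some participants may have no disease in one or more of the four regions at Day 1, and treatment may clear others. Any blank severity item in such a region is tied to low or cleared disease, so losses from this source would be selective rather than random. A fully clear participant, whose EASI is 0, could be recorded as missing.

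A lost Day 1 score does most damage. SAP 5.2 takes baseline as the last non-missing value before the first application, and no earlier EASI is scheduled. Without an unscheduled pre-dose EASI, the participant has no change, percent change or EASI-75 at any later visit.

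**Working it through.** **1. Reproduce the stated range.** SAP 12.4.3 says that the EASI "is a composite score ranging from 0 to 72". The weights are 0.1, 0.2, 0.3 and 0.4. With every severity grade 3 and every area score 6, the total is (0.1 + 0.2 + 0.3 + 0.4) × (4 × 3) × 6 = 72. With every area score 0, it is 0. The stated range is reproduced.

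**2. Does an area-0 region affect the score?** Regional term = weight × (E + I + Ex + L) × A. With A = 0 the term is 0 for any severity grades.

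Worked example, with values chosen for illustration:
- Head: area 0, contributes 0
- Trunk: area 0, contributes 0
- Upper extremities: area 2, grades 2, 2, 1, 1, so 0.2 × 6 × 2 = 2.4
- Lower extremities: area 1, grades 1, 1, 1, 1, so 0.4 × 4 × 1 = 1.6
- EASI = 2.4 + 1.6 = 4.0

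The total stayed at 4.0 when the head and trunk grades were set to each value from 0 to 3 in half steps. With all four areas 0, the total is 0 whatever grades are recorded. Under the current rule, one blank severity item in an area-0 region makes either score missing.

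**3. Does another rule recover the value?** None was found. SAP 6.2 bars imputation, but multiplying by a recorded 0 imputes nothing. The SAP is less strict elsewhere: Appendix 3 scores a TSQM-9 domain with one item missing, and 12.4.2 takes the TEWL median from whatever readings exist.

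**4. What would EASI-75 show if cleared responders were voided?** The documents give no frequency of blanks, so this is an illustration only. Assume N = 48 (the planned number), 30 true EASI-75 responders, and k of those responders voided.

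| k | Observed-case denominator, (30 − k)/(48 − k) | Population denominator, (30 − k)/48 |
|---|---|---|
| 0 | 62.5% | 62.5% |
| 3 | 60.0% | 56.3% |
| 6 | 57.1% | 50.0% |
| 10 | 52.6% | 41.7% |
| 15 | 45.5% | 31.3% |

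At k = 0, which includes the case where zeros are always entered, there is no effect. For scale, the Clopper-Pearson 95% CI at k = 0 is 47.4% to 76.0%.

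The downward direction holds for voided responders. If 3 non-responders were voided instead, the observed-case figure would rise to 30/45 = 66.7%, and the population figure would stay at 62.5%.

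**The case against.** The strongest reply is that the rule may never be triggered. Appendix 4 says that all four sites are assessed for all four signs and provides a grade of 0, so an uninvolved region has a defined, recordable entry. The EASI form, its completion guidelines and its edit checks are not in the documents. The protocol does describe assessment by a qualified physician (Section 8.2) and a validated data capture system with source data verification (Section 11.2). If sites enter zeros, or the form requires or fills them, nobody is lost through this mechanism. Requiring complete items is also a recognisable conservative choice. This reply stands, and it makes the consequence conditional. It does not defend the rule itself, which still discards a known value whenever such a blank occurs.

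A reader might infer that clear or limited-area participants do drop out of the EASI results. The documents do not support that. They do not say that items are left blank where area is 0, and a BSA of 1% to 20% can be spread over all four regions. On the Appendix 1 denominator, a voided participant also stays in the EASI-75 result, in effect as a non-responder.

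A reader might also size the loss from an assumed blank rate. With 20 items and an independent 1% rate, 1 − 0.99^20 = 18.2% of scores are voided. With two of four regions clear and the exception in place, 12 items are needed and 1 − 0.99^12 = 11.4% are still lost. At a 0.1% rate the figures are 2.0% and 1.2%. Neither the blank rate nor the number of clear regions comes from the documents, most of the loss would remain after the fix, and independent blanks do not represent blanks concentrated in clear regions. These figures do not measure the problem.

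**Conclusion.** The point holds in conditional form, as an optional improvement. The algebra is certain: a region with area 0 contributes exactly 0, and the Appendix 4 rule would void a determined score if a severity item there were blank. Whether this happens, and how often, cannot be established from the documents.

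If it happens to a cleared responder, EASI-75 is lowered under either denominator: the participant leaves the denominator if the 12.2.5 rule applies, or counts in effect as a non-responder under the Appendix 1 default. If it happens on Day 1, the participant's later change results normally go too.

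The reach is limited to the descriptive EASI results in SAP 12.4.3. The primary PP-NRS endpoint, the secondary endpoints and the sample size do not depend on the EASI.

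**What to change.** Replace the last sentence of SAP Appendix 4 with:

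> If the area score of a region is 0, that region's score is 0 regardless of its severity items. EASI is missing only if an area score is missing, or a severity item is missing in a region with area score above 0.

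The cost is one SAP sentence and one line of derivation code. If the form already forces zeros, the change alters no result; if not, it recovers exact values without imputation. It leaves one other determined case as missing, a blank area score with all four grades 0, which is a defensible caution because the extent was not recorded.

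In the same edit, state in SAP 12.4.3 which denominator EASI-75 uses.
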